#### 2. BODY TEMPERATURE

	Specify the time of	RESULT
	measurement	OF MEASUREMENT
MORNING	HH:MM	••••••••••••••••••••••••••••••••••••••
DAY	HH:MM	°C
EVENING	HH:MM	0°
Additionally	HH:MM	°C
Additionally	HH:MM	°C
Additionally	HH:MM	°C

#### 3. COURSE OF THE DISEASE

	Specify the evaluation time	Based on your subjective evaluation of the disease symptoms, can you say that you have improved so much that you do not need to use the lozenges anymore?
MORNING	HH:MM	YES / NO
DAY	HH:MM	YES / NO
EVENING	HH:MM	YES / NO

Version 1.0 of September 28, 2016 in Russian.

Page 3 of 7

TE_004_ANG_LOZ	THE PATIENT'S DIARY	PATIENT
TE_004_ANG_LOZ	THE PATIENT'S DIARY	PATIENT

#### DAY 3: DD/MM/YYYY

#### 1. USE OF THE STUDY DRUG: ANGAL/ANTI-ANGIN® FORMULA

1 lozenge/No. of	Specify the time of	Did you experience a pain in your throat	Complaints/Notes
administration	administration	during the use of lozenges?	
1	HH:MM	YES / NO	
2	HH:MM	YES / NO	
3	HH:MM	YES / NO	
4	HH:MM	YES / NO	
5	HH:MM	YES / NO	
6	HH:MM	YES / NO	
7	HH:MM	YES / NO	
8	HH:MM	YES / NO	
0	HH:MM	YES / NO	
10	HH:MM	YES / NO	

#### 2. BODY TEMPERATURE

	Specify the time of	RESULT
	measurement	OF MEASUREMENT
MORNING	HH:MM	°C
DAY	HH:MM	°C
EVENING	HH:MM	0°
Additionally	HH:MM	°C
Additionally	HH:MM	°C
Additionally	HH:MM	°C

#### 3. COURSE OF THE DISEASE

	Specify the evaluation time	Based on your subjective evaluation of the disease symptoms, can you say that you have improved so much that you do not need to use the lozenges anymore?
MORNING	HH:MM	YES / NO
DAY	HH:MM	YES / NO
EVENING	HH:MM	YES / NO

Version 1.0 of September 28, 2016 in Russian.

Page 4 of 7

TE_004_ANG_LOZ	THE PATIENT'S DIARY	PATIENT	
TE_004_ANG_LOZ	THE PATIENT'S DIARY	PATIENT	

#### DAY 4: DD/MM/YYYY

#### 1. USE OF THE STUDY DRUG: ANGAL/ANTI-ANGIN® FORMULA

1 lozenge/No. of	Specify the time of	Did you experience a pain in your throat	Complaints/Notes
administration	administration	during the use of lozenges?	
1	HH:MM	YES / NO	
2	HH:MM	YES / NO	
3	HH:MM	YES / NO	
4	HH:MM	YES / NO	
5	HH:MM	YES / NO	
6	HH:MM	YES / NO	
7	HH:MM	YES / NO	
8	HH:MM	YES / NO	
0	HH:MM	YES / NO	
10	HH:MM	YES / NO	

#### 2. BODY TEMPERATURE

	Specify the time of	RESULT
	measurement	OF MEASUREMENT
MORNING	HH:MM	0°
DAY	HH:MM	0°
EVENING	HH:MM	0°
Additionally	HH:MM	°C
Additionally	HH:MM	°C
Additionally	HH:MM	°C

#### 3. COURSE OF THE DISEASE

	Specify the evaluation time	Based on your subjective evaluation of the disease symptoms, can you say that you have improved so much that you do not need to use the lozenges anymore?
MORNING	HH:MM	YES / NO
DAY	HH:MM	YES / NO
EVENING	HH:MM	YES / NO

Version 1.0 of September 28, 2016 in Russian.

Page 5 of 7

TE_004_ANG_LOZ	THE PATIENT'S DIARY	PATIENT
TE_004_ANG_LOZ	THE PATIENT'S DIARY	PATIENT

#### DAY 5: DD/MM/YYYY

#### 1. USE OF THE STUDY DRUG: ANGAL/ANTI-ANGIN® FORMULA

1 lozenge/No. of	Specify the time of	Did you experience a pain in your throat	Complaints/Notes
administration	administration	during the use of lozenges?	
1	HH:MM	YES / NO	
2	HH:MM	YES / NO	
3	HH:MM	YES / NO	
4	HH:MM	YES / NO	
5	HH:MM	YES / NO	
6	HH:MM	YES / NO	
7	HH:MM	YES / NO	
8	HH:MM	YES / NO	
0	HH:MM	YES / NO	
10	HH:MM	YES / NO	

#### 2. BODY TEMPERATURE

	Specify the time of	RESULT
	measurement	OF MEASUREMENT
MORNING	HH:MM	°C
DAY	HH:MM	°C
EVENING	HH:MM	0°
Additionally	HH:MM	°C
Additionally	HH:MM	°C
Additionally	HH:MM	°C

#### 3. COURSE OF THE DISEASE

	Specify the evaluation time	Based on your subjective evaluation of the disease symptoms, can you say that you have improved so much that you do not need to use the lozenges anymore?
MORNING	HH:MM	YES / NO
DAY	HH:MM	YES / NO
EVENING	HH:MM	YES / NO

Version 1.0 of September 28, 2016 in Russian.

Page 6 of 7

TE_004_ANG_LOZ	THE PATIENT'S DIARY	PATIENT
The patient was instructed on the diary of	completion rules. The diary was given to the patient on Day 1 visit.	
Investigator (Full name/Signature)	/Date	
The diary was returned by the patient on time, according to the protocol. The data were entered correctly, all the corrections (if any) were discussed with the patient.		

Investigator (Full name/Signature) \_\_\_\_\_ / \_\_\_\_ Date\_\_\_\_\_

Version 1.0 of September 28, 2016 in Russian.

Page 7 of 7

### 16.4 Appendix 4. A visual analogue scale for sore throat evaluation

VISIT:  $\Box$  1  $\Box$  2  $\Box$  3  $\Box$  unscheduled

Date:

Time:

**Instructions for the patient:** please evaluate the severity of pain in your throat according to a scale of 0 (no pain) to 100 (the worst pain one can ever imagine) and draw a vertical line so that it crossed the scale below at the point corresponding to the pain in your throat at the present moment.

No pain	The worst pain one
0	100 can ever imagine
Investigator	
(Full name/Signature)	/

Version 1.0 of September 12, 2016 in Russian

# 1 Introduction

This trial has been designed and conducted to evaluate the therapeutic efficacy and safety of the study drug Angal, lozenges [menthol], 1.0 mg + 5.0 mg (Sandoz d.d., Slovenia), comparing to ANTI-ANGIN® FORMULA, lozenges, 0.2 mg + 2.0 mg + 50 mg (OOO Valeant, Russia), in the treatment of patients with uncomplicated acute infectious and inflammatory diseases of the pharynx accompanied by a sore throat. The objective of this Phase III trial is to demonstrate the non-inferior therapeutic efficacy of the study drug as compared to the reference product.

This Statistical Analysis Plan was developed in accordance with the following documents:

- Guidelines for examination of medicinal products, Vol. 1. Federal State Budgetary Institution Scientific Center for Expert Evaluation of Medicinal Products under the Ministry of Health of the Russian Federation (eds. A.N. Mironov). Moscow: Grif and K, 2013.
- ICH harmonised tripartite guideline. Statistical principles for clinical trials (E9). Current Step 4 version dated 5 February 1998.
- GCP rules of the Eurasian Economic Union (a draft).

The objective of this Statistical Analysis Plan is more detailed, compared to Section 9 of the trial protocol, description of the main principles of the protocol-based statistical analysis, description of the primary and secondary endpoints analysis methods, as well as other data obtained during the trial.

This Plan stipulates for consistence of the scheduled and conducted statistical analysis to the trial protocol, including definition of the analysis data sets, transformations and calculations for the endpoints, observations quantity needed, etc. No changes in this Statistical Analysis Plan compared to the trial protocol are envisaged.

# 2. Trial endpoints

# 2.1 Primary endpoint

The primary outcome measure was the percentage of patients without a sore throat after 3 days of therapy on Day 4, as evaluated by the Investigator according to the Tonsillopharyngitis Severity Score (TSS), in both Angal and ANTI-ANGIN® FORMULA arms.

TSS, a questionnaire (point scale) for healthcare professionals, is used in clinical practice as well as clinical trials to evaluate dynamic changes of symptoms severity of the infection-inflammatory process in the throat (Bereznoy VV, Riley DS, Wassmer G, Heger M. Efficacy of extract of Pelargonium sidoides in children with acute non-group A beta-hemolytic streptococcus tonsillopharyngitis: a randomized, double-blind, placebo-controlled trial). One of such clinical trials with TSS questionnaire was conducted in 2005 in Germany, ©CRO Applertee AG. A version of TSS ©CRO Applertee AG was adapted for this protocol.

TSS (Tonsillopharyngitis Severity Score) is a questionnaire for evaluation of the following symptoms severity: pharyngalgia, difficulty in swallowing, salivation, hyperemia of pharyngeal mucosa, and body temperature increase according to a 4-point scale:

- 0 = no symptom;
- 1 = insignificant symptom;
- 2 = moderate symptom;
- 3 = significant symptom.

The axillary body temperature increase is rated as follows:

- 0 points: <37.5 °C;
- 1 point: 37.5 to <38.5 °C;
- 2 points: 38.5 to <39.5 °C;
- 3 points:  $\geq$  39.5 °C.

TSS is filled in by the Investigator based on the patient complaints and physical examination data. The Investigator summarises the points obtained for every symptom to obtain a total sum of TSS points. A total sum of TSS points will be evaluated at screening to define the inclusion criteria and evaluate for the baseline level; measure efficacy of the therapy conducted in the both arms at Visit 2 (Day 4); as well as evaluate the disease outcome at Visit 2 (Day 4) and/or Visit 3 (Day 5), if applicable.

## 2.2 Secondary endpoints

- The frequency of  $\geq$ 50% total score reduction according to the TSS questionnaire completed by the Investigator as compared to the baseline in both Angal and ANTI-ANGIN® FORMULA groups at Visit 2 (Day 4).
- Total score reduction according to the TSS questionnaire, as well as a reduction in the symptoms (sore throat, difficulty in swallowing, salivation, erythema, and fever) after a 3-day therapy, at Visit 2 (Day 4), as compared to the baseline total score.
- A period of time required for disappearance of the disease symptoms, determined according to the patient's diary (subjective patient's evaluation), but no more than 5 days during the trial—for patients who have achieved the corresponding outcome.
- A proportion (%) of patients who fully recovered by Day 4 in Group A and by Day 5 in Group B (the outcome of a disease according to the objective evaluation by the Investigator, the total score according to the TSS questionnaire  $\leq 2$ ).
- A change in the sore throat intensity by 100 mm VAS (visual analogue scale filled in by the patient) at the beginning, after 3 days of therapy, and at the end of treatment in both groups.

## VAS (visual analogue scale) to evaluate pharyngalgia severity:

The patient will fill in this scale at every visit to the trial site (Visits 1, 2, 3, where applicable). Calibrated scales 100 mm in length with the relevant measuring instruments will be provided for the clinical trial.

The patients should evaluate their pain severity according to VAS at every visit (if possible, before administration of the painkillers (if those are required) or the study drug/comparator drug).

## 2.3 Evaluation of the study drug safety and tolerance

Safety of the trial therapy is evaluated based on the systemic parameters (systolic and diastolic blood pressure, breathing rate, heart rate, body temperature, ECG), laboratory tests results, frequency of adverse events (AEs) and serious adverse events (SAEs). AEs nature and incidence (allergic reactions, burning sensation, discomfort) at the administration site will be evaluated throughout the trial. Global evaluation of treatment tolerability will be made by the patient and the physician according to the following scale:

Scores	Evaluation
0	Poor

1	Satisfactory
2	Good
3	Excellent

Evaluation of the study drug tolerability by the patient and the physician (points/scores) should be specified in the eCRF at Visits 2 or 3 (where applicable).

## 3 Main provisions for analysis

## 3.1 Study drugs and therapy schedule

The patients were randomized in 1:1 ratio to the following groups:

**Main group:** Angal, lozenges [Menthol], 1 mg + 5 mg (Sandoz d.d., Slovenia): Administration of 1 lozenge with a not less than 2-hour interval until full dissolution in the mouth, up to 6–10 times per day, for 4 days or until full recovery (whichever occurs first during 4 days of therapy).

**Control group:** ANTI-ANGIN® FORMULA, lozenges, 0.2 mg + 2 mg + 50 mg (OOO Valeant, Russia): administration of 1 lozenge with a not less than 2-hour interval, up to 6 lozenges per day, for 5 days or until full recovery (total TSS  $\leq 2$ ) (whichever occurs first during 5 days of therapy).

## **3.2** Serious protocol deviations

A serious protocol deviation (Item 11.3 of the trial protocol) is a deviation, which may, according to the estimate by the Investigator or a person assigned by the Investigator, result into withdrawal of the subject from the trial or withdrawal of his data from the statistical part of the trial. The deviations not referred to as serious ones shall be considered minor protocol deviations.

For the purposes of this analysis, the serious protocol deviations were defined as follows:

Description	Example/Explanation	Efficacy or safety	Excluded from population:
inclusion and non-	Inclusion criterion No. 5: e.g., inclusion of the patient with initial total TSS $< 5$	Efficiency	РР
Violation of the informed consent receipt procedure	Absence of the Informed Consent Form	Safety and efficacy	All

	Informed Consent Form was signed after randomization/initiation of therapy	Safety and efficacy	None
Randomization and study drugs	Prescription of the drug non-consitent with the randomization arm	Efficiency	РР
	Low compliance: the patient missed more than 3 doses of the study drug	Efficiency	РР
Concomitant drugs	The patient used prohibited drugs during the trial (or had used the drugs prohibited by the inclusion/exclusion criteria before the trial initiation)	Efficacy and safety	РР

A final list of serious protocol deviations will be compiled before the statistical analysis start. Every protocol deviation should be evaluated for the patient's exclusion from the PP data set or statistical analysis by the trial Sponsor representative. The decisions adopted and lists of patients included into the relevant data sets must be documented before the analysis initiation.

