# 4.2.2 Trial design flowchart

# 4.2.3 Trial procedures

# 4.2.3.1 Trial procedures in a table form

#### Table 1. Visit schedule

Trial period	Screening/Randomization/Therapy initiation	Treatment		Further follow-up 	Unscheduled visits
Visits	Visit 1	Visit 2  Visit 3 		Visit 4	
Day after initiation of therapy	Day 1	Day 4 Day 5		Day 6/7	
Trial procedures					
Signing of the Informed Consent Form	•				
Demographic data (date of birth, sex, age)	•				
Measurement of weight and height	•				
Medical history	•				
Collection of complaints, actualization of anamnesis	•	•	•		•
Records on the concomitant therapy	•	•	•		•
Evaluation of the throat pain intensity according to VAS by a patient	•	•	•		
Fill-in of TSS questionnaire 	•	•	•		•
Physical examination (including topical examination)	•	•	•		•
Measurement of vital signs 	•	• *	•		•
Hematology 	•	• *	•		
Biochemistry 	•	• *	•		
Urine pregnancy test 	•				
12-lead ECG	•	• *	•		
Evaluation of inclusion/non-inclusion criteria	•				

<sup>1 A follow up visit will be held in the form of a phone contact with the patient to reveal the possible AEs.

<sup>2 In case of premature discontinuation, the follow-up procedures are the same as those at Visit 2.

<sup>3 Only for the Group B patients who did not meet the recovery criteria (total  $TSS \le 2$ ) at Visit 2 (Day 4) and continued the therapy.

<sup>4 Fill-in of TSS questionnaire by the Investigator (scores for every question should be summarized to obtain a total TSS score).

<sup>5 Systolic blood pressure (mm Hg), diastolic blood pressure (mm Hg), breathing rate (per minute), pulse rate (beats per minute), axillary body temperature (°C).

<sup>6 Hb, RBC, WBC with differential, ESR—at the trial site laboratory.

<sup>7 Total protein, AST, ALT, total bilirubin.

<sup>8 For women with the preserved childbearing potential only.

Trial period	Screening/rand omization/ther apy initiation	Treatment		Further follow-up 	Unscheduled visits
Visits	Visit 1	Visit 2 	Visit 3 	Visit 4	
Day after initiation of therapy	Day 1	Day 4	Day 5	Day 6/7	
Trial procedures					
Randomization	•				
Dispensing of the study drugs	•				
Dispensing of the patient's diaries	•				

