# Visit 3 procedures:

- Collection of complaints, actualization of anamnesis;
- Records on the concomitant therapy;
- Physical examination (including oropharynx);
- Measurement of the main vital signs;
- Evaluation of adverse events (including based on results of the throat and pharynx examination);
- Evaluation of exclusion criteria;
- Return of the unused study drug;
- Return of the patient's diary;
- Compliance evaluation (diary completion, administration of the study drugs).
- Hematology;
- Biochemistry;
- 12-lead ECG;

- Protocol No. TE 004 ANG LOZ
  - Global evaluation of treatment tolerability during the trial by the physician and the patient.

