# 4.2.4.4 A follow-up visit (Visit 4)

A follow-up visit shall be conducted by phone to find out about the patient's state and any AEs. A visit 2 days after the therapy completion visit (e.g., on Day 6 or 7, depending on the arm and therapy duration).

Follow-up visit procedures (by phone):

• Evaluation of adverse events (without the throat and pharynx examination).

In case of adverse events, the patient might be invited to visit the trial site.

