# 4.2.4.5 Unscheduled visits

The unscheduled visits will be conducted when necessary, e.g., in case of the index disease deterioration, AEs, or the study drug (Angal or ANTI-ANGIN® FORMULA) intolerability.

Every unscheduled visit, irrespective of its cause, must include the procedures listed below with completion of the relevant eCRF pages (Unscheduled Visit):

- Physical examination (including topical examination);
- TSS evaluation;
- Measurement of the main vital signs (blood pressure, heart rate, breathing rate, body temperature);
- 12-lead ECG (if it has not been done for the last 12 hours);
- Evaluation of adverse events;
- Evaluation of the concomitant therapy.

Other diagnostic and treatment procedures may be conducted depending on clinical situation and upon the Investigator's decision.

Taking into account frequency of visits, unscheduled visits may be conducted on the same days as scheduled ones but in a different time (e.g., in case of worsening the patient may visit the center in afternoon). All procedures for the scheduled visits are identical for the both arms at every trial stage, except for the Group B patients who, if the recovery criteria (total TSS  $\leq$  2) are not met at Visit 2 (Day 4), should continue the trial therapy and visit the trial site for scheduled Visit 3 Day 5).

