# 4.5 Expected duration of the subjects' participation in the trial

Screening period: 1 day;

Treatment period: up to 5 days (including the screening/randomization day);

Follow-up period: up to 2 days.

A maximum duration of each subject's participation: 7 days. A minimum duration of each subject's participation: 6 days (depending on the arm).

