# 6.2.2 **Prohibited prior and concomitant therapy**

The drugs listed below are prohibited for use throughout the trial period:

- 1. Topical drugs (aerosols, sprays, inhalations, gargle solutions, fast-disintegrating tablets/lozenges/pastilles) in the pharynx or nose.
- 2. Systemic, inhalation, or nasal glucocorticosteroids.
- 3. Systemic or topical (intranasal or pharyngeal) antibacterial drugs.
- 4. Anti-viral drugs.
- 5. Immunomodulatory agents.
- 6. Painkillers or antipyretic agents.
- 7. Class I antiarrhythmics.
- 8. Cholinesterase inhibitors (including neostigmine, distigmine, pyridostigmine) and other drugs for myasthenia.

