#### 7.2 Methods and timing for evaluation, recording, and analysis of efficacy parameters

The methods for efficacy criteria evaluation are described in Section 4.2.3.2. The first endpoint is evaluated in the morning at Visit 2 (Day 4, after 3 days of the trial therapy) before the study drugs intake. Other efficacy endpoints are evaluated in terms stated in Section 7.1.

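### The per-protocol exclusion for prohibited drugs has no time limit, so a patient can leave the PP analysis of the Day 4 primary endpoint for a drug taken after that endpoint was scored

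*SAP*

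**What the plan says.** - **The exclusion.** The serious-deviation table in SAP 3.2 has a concomitant-drugs row: "The patient used prohibited drugs during the trial", or used a drug barred by the entry criteria beforehand. The consequence is exclusion from PP. The row does not refer to any visit or assessment.
- **The ban.** Protocol 6.2.2: "The drugs listed below are prohibited for use throughout the trial period". The list includes painkillers, antipyretics, antibacterials and other topical throat products.
- **The length of the trial.** Protocol 4.5 counts follow-up as part of participation: "Follow-up period: up to 2 days". SAP 3.3 and Protocol 9.7 both define PP as completing treatment and follow-up with no significant deviation.
- **The endpoint.** Protocol 7.2 says that the primary endpoint is "evaluated in the morning at Visit 2 (Day 4, after 3 days of the trial therapy) before the study drugs intake".
- **The review.** Under SAP 3.2 a sponsor representative evaluates each deviation for PP exclusion. The final list and the decisions are to be documented before the analysis.
- **The role of PP.** SAP 3.3 and 4.1.2 make ITT the main analysis of the primary endpoint and PP an additional one. The same PP set also serves the secondary endpoints, one of which is recovery by Day 4 in Group A and by Day 5 in Group B (SAP 2.2).

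**The concern.** A PP set is meant to remove patients whose outcome may have been altered by a departure from the protocol. Here the exclusion window stays open after the outcome is fixed. A patient who still has a sore throat on the morning of Day 4 and takes a painkiller that afternoon, or during follow-up, meets the listed criterion. The drug came too late to affect the Day 4 score. Patients still in pain are also the likeliest to take something, so such removals would tend to be failures, and removing failures raises an arm's PP response rate.

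The protocol adds to the difficulty. For Group B, the synopsis directs standard care when signs persist on the last therapy day. There is no matching sentence for Group A, and the SAP does not say that such care is not a PP deviation.

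What is at stake is how the supporting analysis can be read. PP could differ from ITT for a reason unrelated to treatment received before the endpoint.

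**Working it through.** **Order of events**

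1. Morning of Day 4, Visit 2, before study drug: the primary endpoint is scored in both arms.
2. Rest of Day 4, and Day 5 for unrecovered Group B patients: the ban still applies.
3. Day 6/7: follow-up call. The ban and the PP requirement still apply.

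Use in steps 2 and 3 meets SAP 3.2 as written but cannot bear on step 1. Use between Visits 2 and 3 can bear on Group B's Day 5 endpoints, so for those the exclusion is valid.

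**Where later use would be recorded**

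| Contact after Visit 2 | Who | Concomitant therapy recorded? |
|---|---|---|
| Visit 3 (Day 5) | "Only for the Group B patients who did not meet the recovery criteria" (Protocol Table 1) | Yes: "Records on the concomitant therapy" |
| Visit 4 (phone) | Both arms | Not listed; adverse events only (Protocol 4.2.4.4) |
| Unscheduled visit | Both arms, if one occurs | Yes: "Evaluation of the concomitant therapy" (Protocol 4.2.4.5) |
| Adverse-event record | Both arms, if treated | As treatment of the event (Protocol 8.3.4) |

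The only routine difference between arms is Visit 3, which adds about one day of recording for unrecovered Group B patients. After that, capture is the same in both arms.

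**Illustration of size**

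Inputs: Angal 65%, comparator 63%, margin 14.5 points and 128 per arm completing according to protocol (synopsis, Protocol 9.2); two-sided 90% Newcombe interval (SAP 3.10, 4.1.2). Non-inferiority is taken as a lower limit above -14.5 points, as in the alternative hypothesis of SAP 3.9. The fraction f of an arm's Day 4 failures removed is an assumption; the documents give no rate of use, recording or exclusion.

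The plan's own figure comes first. It states 80% power at 128 per arm and one-sided 2.5%. A simulation with the 95% Newcombe interval gives 79.1%, close to that. The 90% interval in the SAP raises the starting power to 87.4%.

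PP rate after removal = p / (p + (1 - p)(1 - f)). For the comparator:

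- f = 0.05: 0.63 / (0.63 + 0.37 × 0.95) = 0.63 / 0.9815 = 0.6419
- f = 0.10: 0.63 / (0.63 + 0.37 × 0.90) = 0.63 / 0.963 = 0.6542

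Expected removals = 128 × 0.37 × f = 47.4 × f. Power is an exact binomial sum: removals in an arm are Bin(128, (1 - p)f), and responders among those left follow a binomial with the PP rate. No Angal failures are removed.

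| Comparator failures removed | Patients | PP difference (points) | PP power |
|---|---|---|---|
| 0% | 0 | +2.0 | 87.4% |
| 5% | 2.4 | +0.8 | 82.5% |
| 10% | 4.7 | -0.4 | 76.9% |

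At the margin (48.5% v 63%), the chance that PP falsely shows non-inferiority falls from 4.9% to 3.4% at f = 0.05 and to about 2% at f = 0.10. Removing 10% of failures in both arms matters little at the planned rates: the PP difference is +1.9 points and power about 87%.

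**Why these fractions are probably upper-end**

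The calculation applies f to all 47.4 expected comparator failures. Visit 3 is only for patients with total TSS above 2. A patient with a mild sore throat and a total of 1 or 2 fails the primary endpoint, counts as recovered, and never attends. In the reference trial tabulated in Protocol 9.2, 27 of 39 active-arm Day 4 failures (69%) were mild; their total TSS is not given. Taking that split as a stand-in, if every mild case had a total of 2 or less, the Visit 3 pool would be 47.4 × 12/39 = 14.6. The 5% and 10% rows would then need 2.4/14.6 = 16% and 4.7/14.6 = 33% of attendees to be removed. If no mild case did, the pool stays at 47.4. Visit 3 patients with total TSS above 2 but no sore throat are responders, and removing them would offset the effect.

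**The case against.** The best defence has four parts.

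- **No planned conclusion depends on PP.** This stands. ITT is the main analysis, and nothing in the plan requires PP to agree with it. A reader might infer that the rule threatens the trial's main conclusion; the documents do not support that.
- **Removal is not automatic.** This also stands. The row sits in a column of examples and explanations, the final list is still to be compiled, and each case is reviewed. Protocol 5.3.1 item 11 refers to therapy that might influence the results, which could be read as a relevance test. But that item governs withdrawal from the trial. It gives the PP review no timing criterion, and the review takes place in an open-label trial with Day 4 outcomes already known.
- **The recording difference is narrow.** It is about one day, and the pool reached may be well below 47. This stands and limits the size. The power figures are illustrations, not forecasts.
- **One patient-level PP set is conventional.** True, but convention does not make a drug taken after scoring relevant to the score.

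A reader might also infer that the rule favours a false finding of non-inferiority. That needs removals mainly in the Angal arm: 10% of Angal failures alone would raise the PP error at the margin to about 11%. The documents do not exclude this, but routine recording after Visit 2 is fuller for the comparator, so they point the other way.

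**Conclusion.** The point holds as a minor fault in a stated rule. As written, SAP 3.2 and the PP definition allow a patient to be dropped from the additional PP analysis of the primary endpoint for a drug that cannot have affected that endpoint. The likelier direction is loss of comparator failures, which moves the PP difference against Angal and does not inflate error. On the assumed fractions, 5% to 10% of comparator failures (2.4 to 4.7 patients) costs about 5 to 10 points of PP power. That rests on 65% v 63%, 128 per arm, no Angal removals, and every removed patient being a Day 4 failure. The true size could be near zero, and the direction cannot be settled from the documents.

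**What to change.** In SAP 3.2, keep the clause on drugs used before the trial and add:

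> For the primary and other Day 4 endpoints, prohibited drugs lead to PP exclusion only if taken before the Visit 2 TSS assessment. For Group B's Day 5 and end-of-treatment endpoints, they do so only if taken before the Visit 3 assessment. In either arm, standard care started after a patient's last efficacy assessment is not a PP deviation.

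Word the follow-up clause of the PP definition in SAP 3.3 to match. Protocol 9.7 carries the same definition and SAP 1 says that no changes from the protocol are envisaged. Record and justify the change as Protocol 9.6 requires: in an amendment, or in the final report with the departure listed in the SAP before the final analysis.

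The cost is small: no extra patients or visits. The PP set may differ slightly between Day 4 and Day 5 endpoints, clock times are needed for drugs started on the day of Visit 2 or 3, and the departure from Protocol 9.7 needs a short written justification.
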